13.0 Withdrawal of Subjects

We do not anticipate that any research participants will be withdrawn from the research study without their consent. If a participant requests to withdraw from the study, we will ask if they are comfortable sharing the reason for withdrawing to ensure that there are no necessary serious adverse events to report to the IRB. Subsequently, we will ask the participant if they are still willing to permit the study team to continue to access their EHR.

14.0 Risks to Subjects

14.1 Reporting Adverse or Unanticipated Events

We do not anticipate any harm with our study procedures. While some topics probed in study assessments and the STRIDE Intervention may be sensitive in nature, no adverse or unanticipated events occurred in previous studies of psychological interventions conducted by our research group. Reportable adverse events would include a breach of confidentiality. Should adverse or unanticipated events occur during the study, a trained study staff member will report the events to the IRB as soon as they are discovered.

14.2 Anticipated Reaction

As this is a low-risk, social/behavioral study, there are no ingested medications, and no biomedical procedures. It is unlikely that participants will be at any risk for physical harm because of study participation. Participants may find some of questions in the questionnaire or

content in the intervention to be emotionally upsetting, and if so, they may experience some distress.

14.3 Reaction Management

The consent form will include all the study procedures, information about potential risks and benefits of participation, and information regarding whom the participant can contact for further questions. It also will state that participation is voluntary, that participants can refuse to answer any question, that they can withdraw from the study at any time, and that study participation is in no way related to their medical care. All study staff will complete the required human subjects training before they can work on any human subject aspects of the study.

If a participant expresses distress during the psychological intervention visits or exit interviews, they will be reassured by the clinician or study staff member conducting the intervention visit or interview that they can stop at any time and that they do not need to continue participating in content or answer interview questions which they find upsetting. They will also be reminded that study participation is voluntary. If participants remain distressed, they will be offered an opportunity to meet with a psychologist in the Psychiatric Oncology Service at the MGH Cancer Center to help address their distress.

For all participant assessments given throughout the study, study staff will review assessments upon receipt from participants for completion and to assess distress. On the HADS, patients who endorse ≥ 11 on even items for a more severe range for depression will be called by qualified study staff (e.g., [name], a licensed clinical psychologist, [name], a licensed clinical psychologist, [name], a licensed clinical social worker, as well as qualified clinical psychology practicum students and fellows). If a participant completes the distress assessment online through the secure REDCap portal, a study staff member will check the responses and notify the PI for follow-up if needed within 72 hours of assessment completion. If a participant completes assessments on paper, study staff will check the responses and notify the PI for follow-up if needed within 72 hours of receipt. If the patient needs further outpatient services for depression, including pharmacotherapy, or is at risk for self-harm requiring hospitalization, study staff will make the necessary referrals for treatment. For example, for patients who are distressed but in no danger to self or others, study staff will refer either to the MGH Oncology Social Work Service or to the MGH Outpatient Psychiatry Department [contact]), including the Cognitive-Behavioral Therapy Program. If suicidality or risk of harm to others is otherwise discovered at any study visit, the participant will be referred to appropriate services. Specifically, in the case that hospitalization is required, study staff will contact and escort the patient to the MGH Acute Psychiatry Service [contact]), with the aid of the MGH Police & Security if necessary [contact]). If a referral for outpatient services is made, or the patient requires escort to the MGH Acute Psychiatry Service, study staff will notify the health care team, including the primary oncologist.

15.0 Potential Benefits to Subjects*

Challenges associated with AET, including side effects, distress, or difficulties with adherence, are common among BCS. We anticipate the STRIDE Intervention will provide potential benefit to participants by teaching and reinforcing skills to manage these challenges. The intervention was directly informed by qualitative interviews with BCS taking AET to ensure the intervention is beneficial and patient-centered. Additionally, run-in period feedback will be used to further inform the intervention for maximum benefit for participants in the RCT. The risk from participation in the study is small (and will be minimized by the procedures outlined above), and the overall risk to benefit ratio is favorable.

16.0 Vulnerable Populations: Not applicable

17.0 Community-Based Participatory Research: Not applicable

18.0 Sharing of Results with Subjects

If a participant expresses interest in learning the results of the study, their contact information will be collected and securely stored by study staff. Upon completion of data collection for the study, study staff will provide interested participants with an abstract of study results.

19.0 Setting

19.1 Location

As previously stated in recruitment and enrollment procedures (Section 5.1), participants will be approached in-person in the MGH Center for Breast Oncology outpatient clinic in the Yawkey Center for Outpatient Care or called after receiving permission from their care team. Participants from other sites will be contacted via phone. Upon approach, in-person or over the phone, study staff will ensure complete confidentiality of all study information and procedures.

20.0 Resources Available

20.1 Team Qualifications

The PI, [name], is responsible for full oversight of the project at MGH and participating institutions. She will be meeting with the CRC on weekly basis (and more often as urgent issues arise) to ensure the study process is being followed accurately and to address potential challenges or issues as they may arise. [name] is a member of the MGH Cancer Outcomes Research Program (CORE). CORE has extensive experience conducting multi-site randomized clinical trials of supportive care interventions in oncology and has the necessary expertise to ensure the success of the proposed project.

20.2 Site Resources

On an average year, 517 women with newly diagnosed breast cancer were treated with AET at the MGH Cancer Center. Based on literature and our initial findings from Phase 1 of this study, we expect up to 40% will have poor adherence and between 20-25% will have distress. Patients will screen in if they are experiencing distress related to AET, adherence, or side effects, they would be eligible for the study; therefore, we estimate the number of eligible patients may range from 104-208 patients per year.

21.0 Prior Approvals: Not applicable

22.0 Recruitment Methods

As described in Section 5.0, all recruitment methods will be centrally located and executed by study staff at the lead site, MGH Boston. Recruitment strategies include EHR screening, the Partners Rally Recruitment Portal, and Provider Referral.

As detailed in Section 26.0, participants will be provided with compensation of up to \$60 total (\$20/assessment) throughout the study for their time to complete study assessments (Appendix 30.19).

23.0 Local Number of Subjects

Each MGH-affiliate site will have a local accrual goal of 10 participants. The lead site, MGH Boston, will have a goal of 75 participants. The overall study accrual goal will be up to 105 participants (run-in, n=5, RCT n=100).

24.0 Provisions to Protect the Privacy Interests of Subjects

As detailed in the Data Safety Monitoring Plan (Section 12.0), all subjects will receive a confidential number identifier. All participants will be identified on study assessments by their number identifier. Identifiers, such as name, will only be used during the initial data retrieval process and can be destroyed once all data records have been obtained and data analysis has been completed as discussed previously.

25.0 Compensation for Research-Related Injury

We do not anticipate any research-related injury due to involvement in this supportive care trial

26.0 Economic Burden to Subjects

Participants will not endure any additional costs as part of their participation in this research study. As such, we do not anticipate any financial burden on study participants. The study intervention visits will not be billed.

Additionally, study participants will be compensated for their time to complete the three study questionnaire batteries (baseline, 12-weeks post-baseline, and 24-weeks post-baseline).

Participants will be compensated up to \$60 (\$20/assessment completed) in the form of a check (Appendix 30.19).

27.0 Consent Process

As stated previously, study staff will consent patients either in-person or over the phone using study scripts. We will follow all the requirements of SOP: Informed Consent Process (CON-100) in obtaining informed consent for study participants.

Electronic Informed Consent Process (EIC): In the event that a potentially eligible patient expresses interest over the phone but will not be in clinic in the near future or receives care at an MGH-affiliate site, study staff will begin the EIC process. Patients will be asked to provide verbal permission and a preferred email address to be sent an email with a link through REDCap (Appendix 30.20). The REDCap link will direct patients to an encrypted REDCap portal; the Electronic/Paperless Consent Template Project will be used. Screen captures of what the EIC REDCap portal looks like are included in Appendix 30.21. This process begins with the patient verifying their date of birth and full name in order to enter the portal. Additionally, this portal will have the electronic (paperless) consent form, exactly identical in content to the paper version, to guide the patient through the consent discussion with study staff over the phone. At any point, if a patient would prefer to receive a hard copy of the consent form, the EIC process will stop and study staff will send the patient two copies of the consent form in the mail with a prepaid envelope to send it back. The patient will be given ample opportunity to ask questions and take their time to consider their participation. From there, patients will digitally sign and date the consent form. The study staff will then sign and date the consent form as the consenting investigator and send a digital or paper copy of the signed consent form per the participant's preference, sent via Send Secure email if digitally or informed and given the opportunity to opt-out of Send Secure using the Partners Send Secure opt-out language. This process has been found to be highly efficient among other psychosocial research studies, including DF/HCC Protocol #17-201 which directly informed this study, and minimizes burden to patients, study staff, and providers.

Enrollment Procedures. DF/HCC institutions will register eligible participants in the Clinical Trials Management System (CTMS) Oncore as required by DF/HCC SOP REGIST-101. Registration must occur prior to the initiation of protocol-specific procedures or assessments.

For registration of patients from DF/HCC institutions, which will be all participants in this study, study staff will complete the DF/HCC protocol-specific eligibility checklist using the eligibility assessment

documented in the participant's EHR and/or research chart. Study staff will confirm that the participant meets all inclusion criteria as described in this protocol and the criteria on the eligibility checklist. Study staff will be responsible for self-randomization of participants (Biostatistician-generated Randomization Scheme: Appendix 30.8) per ODQ request to decentralize non-therapeutic studies under the DF/HCC. MGH study staff will follow DF/HCC Standard Operating Procedure for Human Subject Research Titled *Subject Protocol Registration* (SOP #: REGIST-101) and register the participant on the protocol.

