consent discussion. Study staff will use Appendix 30.1 to notify the patient's clinician of the intended approach. The study staff will initially introduce the study to patients and ask if they are currently taking their AET. If the patient indicates that they are not interested in the study, study staff will collect the reason for refusal, for the purposes of documentation and future study reporting. If the patient indicates that they are interested in the study and are currently taking their AET, the study staff will screen the potentially eligible patient using the study staff screening script (Appendix 30.3). The brief screening questions are intended to assess the fit of the patient for the study. The participant will screen in to the study if she indicates an answer of 4 or above on any of the three brief screening questions. If a patient screens out of the study, study staff may ask the patient for permission to re-approach her some point in the future, as distress and adherence challenges may come and go at different points throughout the course of the medication. If the patient screens in, she will be presented with a detailed, HIPAA-compliant consent form to be signed by each participant following explanations by study staff. The consent form will include all of the study procedures, information about potential risks and benefits of participation, and information regarding who they can contact for further questions (PI: [name]). It also will state that participation is voluntary, participants can refuse to answer any questions, participants can withdraw from the study at any time, and study participation is in no way related to their medical care. If a participant is unable to be approached in-person or consented in-clinic due to external factors, such as lack of clinic space or patient time constraints, the study team may reach out to potential participants over the phone. Prior to initiating phone contact, the study team will utilize the same provider email to assess if the provider has any reservations about the study staff contacting the patient (Appendix 30.1). If the patient does not have an upcoming appointment in clinic, study staff may call the potentially eligible patient using the recruitment phone script and screening script to gauge interest and eligibility (Appendices 30.3 & 30.4). Study staff will not call more than three times total or leave more than two voice messages (Appendix 30.7). If the patient expresses interest and screens in, the study team will begin the electronic informed consent (EIC) process outlined in Section 27.0.

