6.0 Multi-Site Research

6.1 Multi-Site Study Conduct

This study will be conducted at MGH Boston, lead site, and at three MGH satellite sites, Newton-Wellesley Hospital, MGH North Shore, and MGH Waltham. All affiliate sites are on record by the DF/HCC IRB. As detailed in Section 5.0, the study staff at MGH Boston will maintain full responsibility of recruitment and enrollment at MGH Boston and at the MGH-affiliate sites. The MGH Boston study team will communicate with providers at Newton-Wellesley Hospital, MGH North Shore, and MGH Waltham regarding permission to approach patients over the phone, as detailed in section 3.0, and on the progress of the study or any protocol updates. Site-PIs and peripheral study staff at the satellite site may assist with referrals but that is the extent of their role in study conduct. All participants will be registered and enrolled on OnCore through MGH Boston, regardless of where a participant's primary oncologist is located. All participants will complete the intervention and all study procedures through study staff at MGH Boston. A HIPAA waiver was submitted to the DF/HCC and authorization approved for all sites to which the study is open.

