Rationale: Although we considered an attention-matched condition to control for nonspecific intervention effects, we decided against this approach because medication monitoring is likely to improve adherence alone.⁵² Additionally, requesting participation in a placebo intervention adds undue burden to BCS who are coping with emotional and physical sequelae. Finally, an attention control should only be employed if attention would affect the primary outcome. Since no data suggest that attention would improve AET adherence, an attention control would be an added expense and unethical.⁵² Finally, participants who identify as part of a racial/ethnic minority population will be offered the opportunity to participate in a qualitative exit interview to provide feedback on the STRIDE study.

Retention. Strategies to promote retention will include accurate explanations of study expectations during the recruitment process,⁵³ collection of locator information and a secondary contact (Appendix 3.12), a phone check-in to ensure use of MEMS Caps, branding of study materials for project identity, and reimbursement for time (\$20/assessment). Intervention participants will receive a text reminder one day prior to the scheduled ZOOM session (See Section 5.2 detailing Participant Communication).

9.3 *Study Instruments*

The following questionnaires have been specifically selected to reflect the theoretical intervention targets and aims of the study. All participants will complete the baseline questionnaires within four weeks of documented informed consent. If a participant does not complete the baseline questionnaires within this timeframe, she will be re-screened and re-consented, restarting the four-week window. Follow-up assessments will be completed at 12-week (+/- 2 weeks) and 24-week (+/- 2 weeks) from time of baseline completion (Appendix 30.16) Table 3 details the schedule for administering all study instruments. Patient assessments can be found in Appendix 30.16. We anticipate that 15-20% of 12-week assessments will be out

of window for intervention participants, given the occasional delay of coordinating multiple patients' schedules to arrange the intervention groups.

Instrument/Measure:	Screening	Baseline (4-week window from consent)	12-weeks post-baseline (+/- 2-week window)	*24-weeks post-baseline (+/- 2-week window)
Chart review	X			
Adapted NCCN Distress Thermometer	X			

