30.8 Study Randomization Scheme

Elevated				Arm B	
Elevated				Arm C	
Elevated				Arm C	
Elevated				Arm B	
Elevated				Arm C	
Elevated				Arm B	
Elevated				Arm C	
Elevated				Arm B	
Elevated				Arm C	
Elevated				Arm B	
Elevated				Arm C	
Elevated				Arm B	
Elevated				Arm B	
Elevated				Arm C	
Elevated				Arm B	
Elevated				Arm C	
Elevated				Arm C	
Elevated				Arm B	
Elevated				Arm C	
Elevated				Arm C	
Elevated				Arm B	
Elevated				Arm C	
Elevated				Arm B	
Elevated				Arm B	
Elevated				Arm C	

Randomization sheet for 18-603 - Not Elevated Distress				
Symptom Targeted Randomized Intervention for Distress and Adherence to Adjuvant Endocrine Therapy among Breast Cancer Survivors				
Stratification factors: Distress (elevated or not elevated)				
Treatment codes				
Arm B:	Intervention			
Arm C:	Control			
Distress level	Patient name	Sequence no.	Date entered	Treatment assignment
Not elevated				Arm C
Not elevated				Arm C
Not elevated				Arm B
Not elevated				Arm B
Not elevated				Arm B
Not elevated				Arm C
Not elevated				Arm B
Not elevated				Arm C
Not elevated				Arm B

Not elevated				Arm C	
Not elevated				Arm C	
Not elevated				Arm B	

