30.29 Study Introduction Note Content

[This general content will be included with participants' MEMs bottle at the start of the study, prior to randomization, to introduce them to the study and study team and may be tailored further during the study run-in phase.]

The STRIDE Study
Massachusetts General Hospital
[name]
[name]
[name]
[contact]

[Patient Name]
[Patient Address]
[Patient Address]

Dear [Patient Name],

Thank you so much for your participation in the STRIDE study!

You can find the pill bottle that we spoke of enclosed here. Please place all your hormonal therapy pills in the bottle (and do this each time you refill your medication) and continue taking it as usual. Enclosed are instructions on how to use the pill bottle.

If you have an instance where you do not use the pill bottle for whatever reason, please use the enclosed medication log to note the day you took the medication.

Please feel free to contact me at [\[study coordinator email\]](#) or [\[study coordinator phone number\]](#). Alternatively, you can also contact the principal investigator of the study, [name], at [contact] or at [contact] with any related questions.

Sincerely,

[name].

[Study Coordinator]

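### The role that recruits also randomises, from a list printed arm by arm in the protocol, and no concealed release is described

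*Combined protocol and SAP*

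**What the plan says.** **Who does what.** Section 5.1: "the study staff will screen the potentially eligible patient using the study staff screening script". Section 27.0: "study staff will consent patients either in-person or over the phone using study scripts". Section 6.1 centralises the work: "the study staff at MGH Boston will maintain full responsibility of recruitment and enrollment at MGH Boston and at the MGH-affiliate sites". Under Enrollment Procedures in Section 27.0, study staff also complete the eligibility checklist and register the participant, and then: "Study staff will be responsible for self-randomization of participants (Biostatistician-generated Randomization Scheme: Appendix 30.8". The reason given for local randomisation is an institutional request to decentralise non-therapeutic studies.

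**The list.** Appendix 30.8 holds rows for two strata; the sheet for one is headed "Randomization sheet for 18-603 - Not Elevated Distress". It defines Arm B as intervention and Arm C as control. It has columns for name, sequence number and entry date, and the assignment is already printed on each visible row.

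**The order of events.** Section 27.0: "Registration must occur prior to the initiation of protocol-specific procedures or assessments". Section 9.1 takes the stratum from the baseline HADS. Section 9.3: "All participants will complete the baseline questionnaires within four weeks of documented informed consent". Appendix 30.29 says its introduction note goes out with the "MEMs bottle at the start of the study, prior to randomization". Section 14.3 has study staff read completed assessments when they come in.

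**The concern.** Having a biostatistician generate the sequence makes it unpredictable in principle. Concealment is a separate safeguard: whoever decides whether and when a woman enters must not be able to see the next arm. Here the protocol itself carries the sequence, and the role that recruits is told to randomise from it.

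The plan leaves room to act on such knowledge. Section 5.1 allows women who screen out to be approached again and allows repeated recruitment calls. Section 9.3 allows women who miss the baseline window to be re-screened and re-consented. No section fixes the order or the time limit for randomising women who are already registered.

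What is at stake is the comparison between arms on adherence, symptom distress and satisfaction, and on the exploratory scales. Section 11.1 feeds the effect sizes into the power analysis for the efficacy trial. Section 4.0 gives better detection of group differences in secondary outcomes as a reason for raising RCT accrual from 75 to 100.

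**Working it through.** The plan states no figure on this point, so there is none to reproduce. The check sets the procedures side by side, counts the visible list, and asks what staff could know and when.

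1. **Search for a safeguard.** The text on screening, consent, registration and randomisation (Sections 3.1, 5.1, 6.1, 9.1, 27.0; Appendix 30.8) mentions no sealed envelopes, no central or web release and no independent custodian. The only envelope is the prepaid one for returning paper consent forms.

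2. **Visible rows of Appendix 30.8.** Elevated: 25 rows, 12 Arm B and 13 Arm C. Not elevated: 12 rows, 6 Arm B and 6 Arm C. Total 25 + 12 = 37, with the arm printed on every one. Rows may have been lost in text extraction, so nothing is claimed about the full length of the list.

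3. **What the list reveals, by stage.**
   - *Screening and consent.* The HADS has not been given, so the stratum is unknown. Staff with the list see one next arm per stratum.
   - *After registration, before baseline.* The same, for up to four weeks. Other women may use up rows in this interval.
   - *After baseline is received.* Staff have read the HADS and can assign the stratum. With that and the list, the arm on the next row is known before randomisation.

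4. **How firm is the knowledge at consent?** A woman's row is settled when she is randomised. Table 2 plans up to 100 randomised women over Months 7 to 33, which is 27 months: 100 / 27 = 3.70 a month, or 3.70 × 12 / 52 = 0.855 a week. Assume a steady rate and independent (Poisson) arrivals. The chance that nobody else is randomised during a lag of *w* weeks is exp(−0.855*w*):
   - 1 week: 0.43
   - 2 weeks: 0.18
   - 4 weeks: 0.03

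   The position seen at consent therefore often moves before the woman's turn. Before baseline this is an informed guess. The gap after baseline does not depend on this calculation.

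5. **Separate minor point: the stratum rule.** Section 9.1 sets a HADS cut-off of 8 without saying whether it applies to the total or to a subscale. Section 9.3 describes two seven-item parts, with items answered 1 to 4. On the form in Appendix 30.17, six items (2, 4, 7, 9, 12, 14) rise with symptoms and eight fall, and no scoring key is given. Summed as printed, the lowest possible total is 14 × 1 = 14, so a literal total reading would place every woman in the elevated stratum. The lowest subscale sum is 7 × 1 = 7.

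**The case against.** Several points on the other side stand.

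- **One label is not one person.** The documents say study staff throughout. They neither state that the same individuals perform every step nor separate them.
- **A safeguard may exist elsewhere.** SOP REGIST-101 is cited but not supplied. Only the absence of a described safeguard can be claimed.
- **There are records.** Women are registered before assessments, the sheet has a column for entry date, and Section 12.1 requires weekly reports of approaches, consents, enrolment and withdrawals. Selective delay or loss after registration would leave a trail. These records help detect a problem but do not hide the list.
- **The consequence is bounded.** The primary endpoint is feasibility and acceptability, Section 11.1 says the pilot is not powered for group differences, and the efficacy-trial size is also checked against a clinically meaningful difference and the literature. That limits the effect on sizing but does not remove bias from the pilot estimates.

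A reader might infer that the arm is known at consent whenever the two strata show the same next arm. Among visible position pairs this happens in 12 × 6 + 13 × 6 = 150 of 25 × 12 = 300. The documents do not support that inference: rows can be used between consent and randomisation, any two lists near 1:1 agree about half the time, and only part of the list may be visible. No share of women with a known arm at consent is claimed here.

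**Conclusion.** The concern holds as a weakness of the written plan. One role label covers recruitment and randomisation, the sequence is in the protocol, and no concealment step is described. Staff with the protocol could guess at the arm before baseline and could know a registered woman's arm after reading her HADS.

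The between-arm secondary and exploratory estimates are therefore open to selection bias. The documents give no basis for its size or direction, and none is offered. The feasibility and acceptability endpoints are not randomised contrasts and are little affected. A reader might infer that allocation was actually manipulated; nothing in the documents shows this.

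The conclusion assumes that recruiting staff have the protocol with Appendix 30.8 and that no unsupplied procedure hides the list. Confidence is medium for that reason. This should be corrected, but it does not invalidate the pilot. The HADS wording is a lesser, separate ambiguity: it leaves the stratum open to interpretation and does not undo the randomisation.

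**What to change.** Remove the sequence from the protocol and from the files of anyone who recruits.

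**If allocations remain.** Have the biostatistician load a new stratified sequence into REDCap, which Section 12.1 already uses for data management. Release each arm only after consent, registration, baseline HADS and stratum are locked. Randomise registered women in the order in which they complete baseline, and write that order and a time limit into the protocol. The cost is a short amendment and a small set-up effort (our estimate; the documents give no figure), with no extra patients or visits. The downside is a mid-trial change of method that may leave incomplete blocks, if blocks were used, and must be reported.

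**If accrual is complete** (Appendix 30.5 gives a recruitment end date of 5/1/2022). Report who held the list, when each arm was seen and any procedure that concealed it, whether under REGIST-101 or locally. State the lack of described concealment as a limitation on the between-arm estimates. The cost is a paragraph.

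**Separately,** reconcile Section 9.1, the HADS description in Section 9.3 and the form in Appendix 30.17, so that the score and coding behind the stratum are explicit. No threshold or key is proposed here.
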